3 STUDY DESIGN

We will perform a randomized, controlled trial (RCT) with a 12-week delayed start control group in 224 dyads (Figure 1). Dyads will be enrolled in cohorts of 16. After being screened for eligibility, consented (V0), and completing baseline assessments (V1), dyads will be randomly assigned to immediate start intervention ($n=8$ dyads/cohort) or delayed start control ($n=8$ dyads/cohort) groups. A total of 14 cohorts will be enrolled to achieve our target sample size of 224 dyads. Immediate start groups will participate in the livestreaming Moving Together program from their homes for 1 hour, 2 days/week, for 12 weeks, while delayed start groups engage in usual activities. Twelve-week follow-up assessments will be performed in both groups (V2). The immediate start group will then be invited to participate in maintenance classes on a paid basis, while the delayed start group participates in the Moving Together program for 1 hour, 2 days/week for 12 weeks. Twenty-four week follow-up assessments will then be performed in both groups (V3), and the delayed start group will be invited to join the maintenance classes on a paid basis. Those who participate in the maintenance classes will be invited to provide ongoing feedback.

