6 RANDOMIZATION AND BLINDING

6.1 Randomization

Study participants will be enrolled in cohorts (blocks) of 16 dyads and randomly allocated to the immediate start intervention group ($n=8/\text{cohort}$) or the delayed start control group ($n=8/\text{cohort}$). The randomization sequence will be generated in advance by the data manager using a random number generator on a computer and will be stored separately and securely. Research staff will be unaware of the randomization sequence.

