7 STUDY INTERVENTIONS

7.1 Schedule of Intervention Procedures

The Moving Together Intervention includes an Initial Contact call; Home Set-up and Goals Assessment videoconference; two-way livestreaming online group classes offered for 1 hour, 2 days/week for 12 weeks; Monthly Check-Ins; PLIÉ Experience surveys (administered monthly when participants are taking classes); and a Final Evaluation survey. Each step is described in more detail below. The Schedule of Intervention Procedures in the immediate and delayed start groups is shown in the Table below.

The Intervention Team consists of trained Moving Together Instructors/Coaches and a Community Support Coordinator who will work together to accomplish the intervention tasks. In general, the instructor will perform the goals assessment and teach the Moving Together classes, which will consist of verbal instructions, demonstrations, discussions of program themes, and brief explanations for the movements and goals of the program; the community manager will provide technology support and will administer the check-ins and class surveys.

Intervention	Week 0	Weeks 1-11	Week 12	Weeks 13-23	Week 24
Initial Contact	Both groups				
Home Set-Up and Goals Assessment	Immediate start group		Delayed start group		
Moving Together Classes		Immediate start group		Delayed start group	
Monthly Check-Ins		Both groups (weeks 4, 8, 12, 16, 20, 24)			
MOVING Together Class Experience Surveys		Immediate start group (weeks 2, 6, 12)		Delayed start group (weeks 14, 18, 24)	
Final Evaluation Survey			Immediate start group		Delayed start group

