Each Moving Together class will begin with greetings and a brief check-in, to ensure that everyone feels welcomed and acknowledged. Next participants will engage in seated, mindful body awareness movements that involve massaging or tapping all major body parts (including hands, arms, thighs, calves, ankles/feet, belly, back, neck and head) and deep breathing movements (raising arms overhead while inhaling and vocalizing while exhaling). The goal of these movement sequences is to bring participants into awareness of their bodies and breathing in the present moment, and to create a calming ritual that is repeated at the beginning and end of each class. These movements are designed to be relaxing and engaging at the same time. Next participants will engage in a series of seated, standing and/or paired movements (i.e., performed with their partner) that focus on increasing capacity to perform movements that are most needed for daily function, such as increasing range of motion, reaching, turning, transitioning smoothly between sitting and standing, and balancing while standing and walking. These movement sequences will build slowly in complexity over the course of the program, depending on the functional ability levels of each class. Whenever possible, we will strive to group dyads with similar levels of physical or cognitive abilities. Finally, each class will end with repetition of the mindful body awareness and breathing movements and an invitation for participants to share what makes them feel grateful, appreciative, joyful or happy. The goal in this section of the program is to facilitate positive emotions and feelings of social connection.

Over the Intervention period of 12 weeks/24 classes, the Moving Together program will gradually and methodically progress participants through safe, functional movement sequences from simple to more complex while deepening self-awareness and mindfulness skills and building social engagement and connection through the Moving Together online video class portal.

The Instructor will adapt the program based on feedback and observations during class, Monthly Check-In data, and Moving Together Class Experience survey responses.

The final day of class will include a graduation. Participants will receive a graduation certificate in the mail prior to that day.

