7.2.7 Delayed Start Control

The delayed start control group will be encouraged to continue with their usual daily activities while they wait for their classes to begin.

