10.2 Sample Size and Power

To be conservative, power estimates were based on an unpaired t-test analysis with two-sided alpha=0.05. A sample size of 224 (112/group) will provide us with 80% power to detect a clinically meaningful standardized effect size of 0.375 to test Hypothesis 1a.

Assuming 20% attrition, we would have 80% power to detect a standardized effect size

of 0.395. For hypothesis 1b, we will be able to conduct exploratory analyses using the full sample of 224, since both groups will receive the intervention and will be offered the opportunity to participate in maintenance classes. Again assuming 20% attrition, a final sample of 179 will provide 80% power to detect correlation coefficients as small as 0.20.

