10.3 Data Analyses

We will examine distributions of all variables to assess for missingness, outlier values or skewed distributions using standard techniques (e.g., means, medians, standard deviations, ranges, tables, graphical techniques). We will assess balance between the immediate and delayed start groups by comparing baseline characteristics (e.g., means \pm SD, N [%]). If meaningful differences occur by chance, we will perform sensitivity analyses adjusting for these differences.

Our primary analytic approach will be linear mixed models (LMMs) with terms included for group, time, and group*time interaction with random intercepts and slopes. This approach will enable efficient estimation of change in primary outcomes over time while including all participants randomized (intent-to-treat) and accounting for baseline values and correlations between repeated measures over time. Milestone 1a will determine if there is a significant group*time interaction for our primary outcome of quality of life, with separate analyses performed for PWML and CGs. Milestone 1b will involve exploratory analyses to examine potential mechanisms of action. These will include using PROCESS to assess for indirect effects (mediation) and contingent effects (moderation) based on baseline characteristics of our study participants (e.g., age, sex, caregiving relationship) and changes in secondary outcomes (e.g., mobility, well-being, isolation). Exploratory analyses also will examine the impact of 'dose' (based on class attendance), and sensitivity analyses will be restricted to those with high compliance ($\geq 75\%$ class attendance). For covariates that have more than 10% missing data, we will consider using multiple imputation.

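### The primary model has no cohort or class term and the power calculation has no clustering allowance; if classes share an effect, the group-by-time test is too liberal by an amount that depends on an unstated ICC

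*Combined protocol and SAP*

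**What the plan says.** - **Randomisation.** Section 6.1: "Study participants will be enrolled in cohorts (blocks) of 16 dyads and randomly allocated to the immediate start intervention group", with 8 dyads per arm in each cohort. Section 3: "A total of 14 cohorts will be enrolled to achieve our target sample size of 224 dyads".
- **Delivery.** Section 7.1 describes "two-way livestreaming online group classes offered for 1 hour, 2 days/week for 12 weeks". Section 7.2.3 makes the pace of progression depend on the ability level of each class and adds: "The Instructor will adapt the program based on feedback and observations during class". On class composition it says: "Whenever possible, we will strive to group dyads with similar levels of physical or cognitive abilities".
- **Control arm.** Under Section 7.2.7, delayed-start dyads are to "continue with their usual daily activities while they wait for their classes to begin". They therefore attend no class before the 12-week visit (V2), but have attended by the 24-week visit (V3).
- **Analysis.** Section 10.3 specifies a linear mixed model with group, time and group*time, and random intercepts and slopes. It does not name the level of the random effects, but the stated purpose, "accounting for baseline values and correlations between repeated measures over time", points to the participant. Cohort, class and instructor are not mentioned, and the section does not say which group*time contrast over the three visits is the test.
- **Power.** Section 10.2: "power estimates were based on an unpaired t-test analysis with two-sided alpha=0.05". It gives 224 dyads (112 per group) and 80% power at a standardised effect of 0.375. It states no ICC or design effect.

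**The concern.** Randomising individual dyads does not remove correlation that arises afterwards. Dyads in one class share an instructor, a pace and a social group, and Sections 5.3.3 and 10.1 list social relationships among the hypothesised routes to better quality of life. If a class effect follows, outcomes within a class are positively correlated and the immediate-arm mean is less precise than the model believes. At V2 this can happen only in the immediate arm; by V3 it can happen in both.

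Cohort and class act differently. Cohort is the randomisation block, and leaving it out makes the test slightly conservative. Leaving out a real class effect makes the test liberal. Milestone 1a uses the same model for persons with memory loss and for caregivers, so both primary outcomes are exposed.

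**Working it through.** **Inputs from the documents:** 112 dyads per arm, 14 cohorts, 8 + 8 per cohort, two-sided alpha 0.05, effect 0.375, attrition 20%.

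**Assumptions made here:** class ICC 0.01, 0.02, 0.05 or 0.10; one class of *m* = 8 per cohort arm, with *m* = 4 as the alternative; the V2 contrast as the test.

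**1. The plan's own figure.** n per arm = 2 × (1.960 + 0.842)² / 0.375² = 111.6, rounded up to 112. Power at 112 per arm = Φ(0.375/√(2/112) − 1.96) = Φ(2.806 − 1.96) = 80.1%. The figure reproduces, with independent dyads.

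**2. Variance with clustering in one arm.** The immediate-arm mean has variance [1 + (m−1)·ICC]/112 and the control mean 1/112. The sum is (2/112)·F, where F = 1 + ((m−1)/2)·ICC. If an omitted cohort-by-time share *c* is also present, F = 1 − c + ((m−1)/2)·ICC.

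**3. Formulas.**
- Type I error of the test that ignores class = 2·[1 − Φ(1.96/√F)]
- Power with the correct standard error = Φ(0.375/√((2/112)F) − 1.96)
- Effect detectable with 80% power = 2.8016·√((2/112)F)

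**4. Results, classes of 8, c = 0.**

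| ICC | F | Type I error | Power at 0.375 | Detectable effect |
|---|---|---|---|---|
| 0.01 | 1.035 | 5.4% | 78.8% | 0.381 |
| 0.02 | 1.070 | 5.8% | 77.4% | 0.387 |
| 0.05 | 1.175 | 7.1% | 73.5% | 0.406 |
| 0.10 | 1.350 | 9.2% | 67.6% | 0.435 |

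Power and detectable effect are before attrition and before any gain from baseline values.

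**5. How far the assumptions move type I error** (ICC 0.01/0.02/0.05/0.10).
- Classes of 4 (F = 1 + 1.5·ICC): 5.2/5.3/5.9/6.8%.
- 20% attrition, so 8 × 0.8 = 6.4 analysed per class (F = 1 + 2.7·ICC): 5.3/5.6/6.6/8.2%.
- Classes of 8 with an assumed c = 0.05 (F = 0.95 + 3.5·ICC): 4.8/5.2/6.5/8.6%. Net inflation starts only above ICC = 0.05/3.5 = 0.014.

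**6. Simulation checks.** A V2 t-test ignoring class, with 14 cohorts of 8 + 8 and 20,000 runs, rejected about 5.6/6.9/9.4% at ICC 0.02/0.05/0.10. With a cohort effect of 5% of variance and no class effect it rejected about 4.5%. The three-wave mixed model (categorical time, assumed V1–V2 correlation 0.58, 3,000–4,000 runs) gave 7.3% at ICC 0.05 and 8.6–10.1% at 0.10 for the V2 contrast. The joint two-degree-of-freedom interaction gave 8.9–10.1% and 12.4–14.4%. The choice of contrast therefore matters.

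**7. Does ability grouping cause the problem?** With dyads fully sorted on baseline into classes of 4 within each cohort arm, and no true class effect, the test ignoring class rejected 4.9% and a class-level test 3.3%. Sorting dyads already randomised leaves the arm mean, and hence its variance, unchanged.

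**The case against.** **The size is assumed.** The documents give no ICC and no class size, and nothing in them shows that 0.05 is plausible. Section 7.2.2 also tailors the programme to each dyad, which works against a shared class effect. This stands: the documents establish an unstated assumption, not a demonstrated error.

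**Ability grouping.** A reader might infer from Section 7.2.3 that grouping similar dyads in itself makes the standard error too small. Step 7 shows that it does not; a shared effect arising in the class is needed. There is also a tension: with one class of 8 per cohort arm, randomisation fixes membership and no sorting can occur. If sorting does occur, classes are smaller or mix cohorts, and the figures for 8 do not apply.

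**The t-test was chosen to be conservative.** Section 10.2 says so, and the planned model uses baseline values. If 0.375 and the ICC are scaled to the V2 standard deviation, and the V1–V2 correlation is 0.58 (neither is stated), change has variance 2(1 − 0.58) = 0.84. Replacing F by 0.84 + 3.5·ICC gives power of about 85/84/80/73%. The power losses in step 4 may therefore be recovered in whole or part. Type I error is not repaired this way.

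**The remedy has costs.** A class term can be over-conservative, and one that is active in a single arm could unblind the statistician, whom Section 6.2 keeps to Group A/B labels. Both objections stand and are addressed in the fix.

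**Conclusion.** The point holds as a gap in the specification. Sections 10.2 and 10.3 make no provision for class or cohort, although the design creates both. If a shared class effect arises, the group*time standard error is too small. With classes of 8 the inflation is modest at ICC 0.01–0.02 (5.4–5.8%) and material from about 0.05 (7.1%, rising to 9.2% at 0.10). With classes of 4 it stays at or below 6.8% over the same range. Near ICC 0.01, with a cohort-by-time share of 0.05, there is no net inflation.

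A reader might go further and conclude that the primary test is invalid, that 224 dyads are too few, or that omitting cohort inflates error. The documents do not support these readings. The ICC is unknown, the stated sample size is correct under its own assumption, and omitting cohort acts in the conservative direction. The change should be made because it is cheap now and would be a post hoc choice after unblinding. Confidence in the size is medium.

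**What to change.** **Section 10.3**
- Name the group*time contrast that is the test, for example the V2 contrast.
- Add cohort and cohort-by-time to the model, and a random effect for assigned class that is active once an arm has started classes. Use small-sample degrees of freedom and retain baseline values.
- Define class by assignment, not attendance, so that all randomised dyads stay in. The class list that Section 8.2 has instructors prepare before the first class could supply it. That list serves safety, so assigned class must also be recorded as a coded analysis variable; a dyad that never starts keeps its scheduled class.
- Lock the code before class labels are released, so that the statistician stays blinded.
- Name the test on the 14 within-cohort differences in mean change (13 df) as a sensitivity analysis, or as a fallback only under a pre-stated trigger such as non-convergence. It uses only dyads with observed follow-up and does not apply if classes mix cohorts.

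**Section 10.2**
- State an assumed ICC range and give power or detectable effect over it, with enrolment unchanged.

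**Cost.** SAP wording, model code and one recorded variable; no extra participants or visits. Stated power becomes less favourable and intervals somewhat wider.
- *Proposed model, simulated at V2 only:* power 76.8% with no clustering and 76.4/72.4/66.2% at ICC 0.01/0.05/0.10; type I error 3.6–6.2%. It can be conservative when the class ICC is near zero or classes are sorted by ability (about 3.3% for the class-level test with fully sorted classes of 4). If the named contrast uses V3, check its error rate before the code is locked.
- *13-df test:* power 73.7% with no clustering and 66.8% at ICC 0.05; intervals about 10% and 19% wider respectively than those of the unclustered t-test.

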10.4 Interim Analyses and Stopping Rules

No interim data analyses are planned. The SO or NIA PO may request that an interim analysis be performed at their discretion. If interim analyses are requested, criteria for stopping the study will be clearly defined in advance by SO and NIA PO.

11 DATA COLLECTION AND QUALITY ASSURANCE

11.1 Data Collection Forms

Our primary approach to data collection will be online surveys administered through REDCap or Qualtrics, with data stored on the UCSF network (e.g., in REDCap or project-specific MyResearch folders). If participants prefer, questionnaires may also be completed by telephone or email, or paper forms may be sent through the mail. For PWML, assessors may assist participants with online questionnaire completion (for example, by sharing a screen with the questions shown, and entering responses for them).

11.2 Data Management

UCSF is responsible for collection and secure storage of all research data. A REDCap database will be created to enable research staff to track enrollment of study participants, collection of outcome data, and delivery of the intervention. Access to the database will be restricted to the research team. In addition, the enrollment and assessment team will not be able to see or access the intervention section of the database, and the intervention team will have read access only to the enrollment and assessment section of the database. The outcomes section of the database will not include any protected health information (PHI) and will identify participants by unique personal identification numbers (PIDNs) only.

Sharing permissions will be configured to ensure files containing PHI can only be accessed by authorized individuals. Two-step verification will be used as an additional safeguard against unauthorized access. Permissions will be updated when personnel roles change and they no longer need access to PHI or when they leave the research team.

Digital signatures will be obtained using DocuSign or REDCap. Paper copies of consent forms, signatures, or other research-related documents will be stored in locked file cabinets. Electronic data may be collected using REDCap or Qualtrics or stored in UCSF's MyResearch environment in a folder that is accessible only to approved research team members.

11.3 Quality Assurance

11.3.1 Training

New research team members will be trained by having them first review current versions of the Study Protocol and Manual of Operations (MOP). They will observe senior team members engaging with study participants and will then practice with senior team members through role play. Senior team members will then observe them interacting with study participants and provide feedback until they achieve competency. Competency will be reassessed annually or more frequently if needed.

Any documents containing personally identifying information (e.g., names and contact information for potential study participants) will be sent by encrypted email.

All study staff will be trained by the same lead person in the same manner. [name] will train staff in administering assessments. [name] will train the interventionists. Each lead will also monitor performance and provide feedback to ensure consistency.

11.3.2 Monitoring

The database manager, supervised by the PIs, will enact and monitor data quality control checks. Data quality control checks will be included to identify potential data anomalies such as:

- Missing data or forms
- Out-of-range or erroneous data
- Inconsistent and illogical dates over time
- Data inconsistency across forms and visits
- Not completing all fields of a "completed form" or no reason for missing data is provided

The data entry forms will include logic and range checks to minimize the possibility of missing or invalid entries. Electronic data entry forms will mirror paper case report forms. Calculations will be automated whenever possible.

At the end of each outcome assessment, research staff will review all questionnaires to check for incomplete data and logical inconsistencies. Whenever possible, errors will be identified and corrected in the moment. If incomplete data or logical inconsistencies are discovered later, research staff may follow up with study participants to clarify if possible. Otherwise, those items will be entered as missing.

12 PARTICIPANT RIGHTS AND CONFIDENTIALITY

12.1 Institutional Review Board (IRB) Review

The UCSF IRB will serve as the IRB of record for this study. They will review and approve the initial Study Application, on which this Study Protocol is based. In addition, they will review and approve all patient-facing materials and scripts such as recruitment materials, telephone screeners, informed consent documents, and intervention-related scripts. All modifications of these documents will be reviewed and approved by the IRB before being used with study participants.

12.2 Informed Consent Forms

All study participants will sign informed consent documents or will assent to having a legally authorized representative sign on their behalf. Signatures may be on paper forms or may use DocuSign or REDCap. The consent form will describe the purpose of the study, the procedures to be followed, and the risks and benefits of participation. Some participants may be concerned about loss of privacy associated with other participants and the group-based format of the intervention. Each dyad will receive a copy of the consent form in paper or electronic form.

12.3 Participant Confidentiality

All research team members will complete mandatory trainings in human subjects research and confidentiality required by the UCSF IRB, including training to ensure Health

Insurance Portability and Accountability Act (HIPAA) compliance. All forms and study procedures are reviewed by UCSF's IRB for compliance with HIPAA and human subjects protections. Any data that will be accessed or disclosed outside the research team will meet HIPAA requirements, through the use of business associate agreements, data use agreements, de-identification, and/or accounting of disclosures, as applicable.

Research team members will be required to use computers that require passwords and DUO authentication to access the research database and participant PHI.

